3.1.2 Study Day

Study Day will be calculated from the date of tezepelumab dosing (Day 1) and will be used to derive start/stop day of assessments and events, with the exception of concentration-time data and derived PK parameters.

If the date of the assessment/event is on or after the date of tezepelumab dosing, then:

- Study Day = (date of assessment/event – date of tezepelumab dosing) + 1.

If the date of the assessment/event is prior to the date of tezepelumab dosing, then:

- Study Day = (date of assessment/event – date of tezepelumab dosing).

3.1.3 Study Period

The following study periods are defined for analysis purposes:

- Screening period: starting on the date of obtaining informed consent/assent, and ending one day prior to IP administration.
- On-study period (treatment and follow-up): starting on the date of IP administration and ending on the study completion or date of withdrawal from study.

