8.3.2 Follow-up of AEs and SAEs

Any AEs that are unresolved at the subject's last AE assessment or other assessment/visit as appropriate in the study are followed up by the Investigator for as long as medically indicated, but without further recording in the eCRF. AstraZeneca retains the right to request additional information for any subject with ongoing AE(s)/SAE(s) at the end of the study, if judged necessary.

Adverse event variables

The following variables will be collected for each AE:

- AE (verbatim)
- Severity
- The date when the AE started and stopped
- Whether the AE is serious or not
- Investigator causality rating against the IP (yes or no)
- Action taken with regard to IP
- AE caused subject's withdrawal from study (yes or no)
- Outcome.

In addition, the following variables will be collected for SAEs:

- Date AE met criteria for serious AE
- Date Investigator became aware of serious AE
- AE is serious due to
- Date of hospitalisation

- Date of discharge
- Probable cause of death
- Date of death
- Autopsy performed
- Causality assessment in relation to Study procedure(s)
- Causality assessment to other medication.

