9.4.3 Safety

Safety analyses will be performed using the safety analysis set. Safety data will be presented using descriptive statistics unless otherwise specified.

Verbatim terms of AEs will be coded to a standardised PT using the MedDRA version in force at DBL.

The overall number and percentage of subjects with AEs and SAEs will be presented. The occurrence of AEs and SAEs will be described also by SOC, PT and separately by severity and by relationship to the IP (as determined by the Investigator). Should a subject report the same PT/SOC within multiple severity or relationship categories, the subject's worst occurrence (most severe/most related) will be tabulated.

Serious AEs, AEs leading to death, AEs leading to withdrawal from study, commonly occurring AEs and AESIs will be summarised by SOC and PT.

Laboratory data, including serum chemistry, haematology and urinalysis will be summarised by presenting summary statistics of observed and change from baseline values at each scheduled assessment visit. Shift tables using normal ranges (baseline to most extreme postbaseline value) will also be presented. The incidence of clinically notable laboratory abnormalities will be summarised. Shift tables will also be provided.

Number of subjects with elevated liver function tests that meet the HL definition will be summarised and evaluated.

Vital signs data will be summarised by presenting summary statistics of observed and change from baseline values at each scheduled assessment visit. The incidence of clinically notable vital signs abnormalities will be summarised.

Abnormal ECGs as per Investigator's overall interpretation will be summarised using frequency and percentage of subjects.

Additional analyses assessing the impact of COVID-19 may be included in the SAP.

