3.4.1 Adverse Events

Adverse events (including SAEs) experienced by any subject at any time during the entire study will be coded using the latest version of the Medical Dictionary for Regulatory Activities (MedDRA) at the time of database lock.

Adverse events will be categorised for analysis according to their onset date into the following study periods described in Section 3.1.3:

- AEs occurring during the screening period: date of informed consent \leq AE onset date $<$ date of dose of IP,
- AEs occurring during the on-study period: date of dose of IP \leq AE onset date \leq date of study completion or date of withdrawal from study.

If the AE has a completely missing (and unresolvable) onset date, then the AE will be considered an on-study event, unless the end date indicates unambiguously that the AE resolved before treatment started. If the AE has a partially missing (and unresolvable) onset date, then the AE will also be considered an on-study event, unless either the end date indicates unambiguously that the AE resolved before treatment started, or the imputed partial onset date is prior to start of treatment.

The handling of partial/missing dates for AEs is detailed in [Appendix A](#).

Adverse Events of Special Interest

Certain preferred terms, groups of preferred terms, or standardised MedDRA queries (SMQs) are being identified as being of special scientific and medical interest towards improving the understanding of tezepelumab. The list of terms used to identify adverse events of special interest (AESIs) may be updated on an ongoing basis as new safety data are accumulated.

The protocol specifies Adverse Events of Special Interest (AESIs) as those which merit special attention in this trial, and for which derivation details (for those derived from the eCRF), or a statement when the derivation needs to be referenced externally to the SAP (for those derived from MedDRA dictionary terms), are given in [Appendix B](#).

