4.2.6.1 Adverse Events

All AEs experienced by the subjects will be collected throughout the study, as per CSP Table 1, and will be coded by IQVIA using the latest version of MedDRA at the time of database lock.

Adverse events and SAEs will be categorised for analysis according to their onset date into occurring during the screening period or the on-study period. Adverse events occurring during the screening period will only be presented in the subject listing. Adverse events occurring during the on-study period will be summarised and listed as follows:

An overall summary table will be produced showing the number and percentage of subjects with at least one AE in each of the following categories: any AEs, SAEs, AEs with outcome of death, and AEs leading to withdrawal from study. The total number of AEs in the different AE categories in terms of AE counts will also be presented (i.e. accounting for multiple occurrences of the same event in a subject).

Adverse events, SAEs, AEs with outcome of death, AESIs and AEs leading to withdrawal from study will be summarised by SOC and PT assigned to the event using the MedDRA dictionary by descending frequency order. For each PT, the number and percentage of subjects reporting at least one occurrence of the event will be presented (i.e. subjects with multiple occurrences of the same PT will only be counted once).

Adverse events and SAEs will be summarized by PT and Investigator's causality assessment (related versus not related) and maximum intensity. If a subject reports multiple occurrence of the same AE within the same reported period, the maximum intensity will be taken as the highest recorded maximum intensity (the order being severe, moderate, and mild).

Separate listings of subjects with AEs, SAEs, AEs with outcome of death and AEs leading to withdrawal from study will be presented.

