A subject will be considered to have this AESI if the subject has at least one preferred term with AE onset date during the relevant study period for analysis, which satisfies the following:

- “AE Category” on Adverse Events eCRF page marked as “Severe Infection”, and one or more of the following:
 - AE is serious (“Serious” on Adverse Events eCRF page marked as “Yes”), or
 - AE required treatment with systemic antiviral medications, intravenous antibiotics or medications for Helminth parasitic infection.

Injection site reactions

Injection site reactions will use an investigator-driven definition, i.e. will be directly determined from what is entered on the eCRF.

A subject will be considered to have this AESI if the subject has at least one preferred term with AE onset date during the relevant study period for analysis, which has “AE category” on the Adverse Events eCRF page marked as “Injection Site Reaction”.

Opportunistic infections

Opportunistic infections will be defined using a pre-specified list of preferred terms (AZ defined SMQ).

AESIs and related definitions based on MedDRA terms are not included in this SAP to facilitate their maintenance (e.g. management of MedDRA version changes), and for convenience in using them directly in SAS programming. These detailed definitions will be finalised by the study team prior to the primary database lock and provided together with the study datasets at the time of submission.

Guillain-Barre syndrome

Guillain-Barre syndrome will be defined using an SMQ.

AESIs and related definitions based on MedDRA terms are not included in this SAP to facilitate their maintenance (e.g. management of MedDRA version changes), and for convenience in using them directly in SAS programming. These detailed definitions will be finalised by the study team prior to the primary database lock and provided together with the study datasets at the time of submission.

SIGNATURE PAGE

This is a representation of an electronic record that was signed electronically and this page is the manifestation of the electronic signature

Document Name: d5180c00025-SAP-v2.0		
Document Title:	d5180c00025 Statistical Analysis Plan v2.0	
Document ID:	CCI [REDACTED]	
Version Label:	2.0 CURRENT LATEST APPROVED	
Server Date (dd-MMM-yyyy HH:mm 'UTC'Z)	Signed by	Meaning of Signature
02-Aug-2022 09:13 UTC	PPD [REDACTED]	Content Approval
02-Aug-2022 11:45 UTC	PPD [REDACTED]	Content Approval
02-Aug-2022 09:27 UTC	PPD [REDACTED]	Author Approval

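### An adverse event that starts in screening and first becomes serious after the dose is left out of the SAP's AE and SAE summary tables

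*SAP*

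**What the plan says.** SAP 3.1.3 defines the periods: "Screening period: starting on the date of obtaining informed consent/assent, and ending one day prior to IP administration". The on-study period begins on the date of dosing. The operative rules come later.

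- SAP 3.4.1: "Adverse events will be categorised for analysis according to their onset date into the following study periods described in Section 3.1.3". If the onset date is missing or partial, the event counts as on-study unless its end date, or the imputed partial onset date, places it before treatment.
- SAP 4.2.6.1 repeats the rule and names SAEs: "Adverse events and SAEs will be categorised for analysis according to their onset date into occurring during the screening period or the on-study period". It then says: "Adverse events occurring during the screening period will only be presented in the subject listing". Only on-study events feed the overall AE summary, the SOC/PT tables (AEs, SAEs, fatal events, AESIs, withdrawals) and the causality and intensity tables.
- SAP Appendix B restricts the AESIs taken from the eCRF (helminth infection, severe infection, injection site reaction) to events "with AE onset date during the relevant study period for analysis".
- Protocol 8.3.2 collects start and stop dates for every AE and, for SAEs, a further item: "Date AE met criteria for serious AE". The SAP does not mention this date.
- Protocol 9.4.3 plans the AE and SAE counts without mentioning a period: "The overall number and percentage of subjects with AEs and SAEs will be presented".

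**The concern.** The protocol has one date for when an event began and another for when it became serious. One AE record can therefore start before the dose and turn serious after it. The SAP sorts on the first date only. Read literally, it treats that event as a screening event and keeps it out of the SAE table, even if the investigator attributes it to tezepelumab.

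A safety objective in children should count harm that reaches the serious threshold after exposure, and Protocol 2.3.1 names serious infections as a potential risk. With about 14 treated children, one event decides whether the report says there were no SAEs or one. The SAP also treats medications differently: under 3.1.5, a drug started before dosing and continuing afterwards is concomitant. AEs have no equivalent carry-over.

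**Working it through.** The plan states no figure to reproduce, because this is a classification rule. The check applies the rule to event patterns and then sizes one misplaced child.

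**Step 1. Inputs.** The period boundary is the dose date (SAP 3.1.3). The sorting variable is AE onset date (SAP 3.4.1, 4.2.6.1, Appendix B). Screening-onset events are listed only (SAP 4.2.6.1). The seriousness date is collected (Protocol 8.3.2). About 14 children are to be dosed and at least 12 are to complete (SAP 1.3).

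**Step 2. Apply the rule.** The alternative also counts a pre-dose-onset event as on-study if its seriousness date is on or after the dose date.

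| Event, with onset date known | SAP rule | Alternative |
|---|---|---|
| Onset Day -5, resolved before dose | listing only | listing only |
| Onset Day -5, first serious Day 10, one record | listing only | AE and SAE tables |
| Onset Day -5, more severe Day 10 but not serious, one record | listing only | listing only |
| Worsening entered as a new record with onset Day 10 | tables | tables |

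The second row is the defect. The third and fourth show that non-serious worsening depends on how it is recorded: the existing rule already captures a new record.

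**Step 3. Which tables are affected.** All summaries built on the on-study AE set in SAP 4.2.6.1, and the investigator-driven AESIs. SAP 4.2.6.2 to 4.2.6.4 build the laboratory, Hy's Law, vital-sign and ECG outputs from post-baseline values or visits, so AE onset plays no part there.

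**Step 4. Size of one misplaced child.** 1/14 = 7.1%; 1/12 = 8.3%. Exact two-sided 95% limits, with the upper limit for 0/n equal to 1 − 0.025^(1/n):

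- n = 14: 0/14 has upper limit 1 − 0.025^(1/14) = 23.2%; 1/14 has limits 0.2% to 33.9%.
- n = 12: 0/12 has upper limit 1 − 0.025^(1/12) = 26.5%; 1/12 has limits 0.2% to 38.5%.

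**Step 5. How often.** The documents give no frequency for this pattern. For a rough ceiling, assume the adolescent SAE incidences quoted in Protocol 2.2 (2.4% tezepelumab, 4.9% placebo, in a 52-week study) apply here and scale with time. Day 1 to Day 85 is 12 weeks.

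- 14 × 0.024 × 12/52 = 0.08 children
- 14 × 0.049 × 12/52 = 0.16 children

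This is the expected number with any SAE after dosing. Only those whose event began before dosing are affected, so the expected number is smaller still. The source population was adolescents with severe uncontrolled asthma, so the figure indicates order of magnitude only.

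**The case against.** The strongest reply is that little is lost in practice. The event stays in the listing, and with 14 children a listing can be read case by case. Protocol 8.3.8 requires every SAE to be reported within 24 hours. Screening and dosing rules also remove many candidates: exclusions 8 and 10 cover significant infection and illness, suspected COVID-19 at Visit 2 means screen failure, and Protocol 6.2.2 withholds the dose for illness judged to compromise safety. All of this stands and keeps the point small. It does not make the SAE table right when a case occurs.

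One could read the onset of an SAE as the date it became serious. SAP 3.4.1 does not support this: it covers AEs including SAEs and compares AE onset date with dose date.

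There are also stronger readings that a reader might infer and that the documents do not support.

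- *That every safety table is affected.* Step 3 shows otherwise.
- *That period assignment can only hide harm.* Missing onset dates default to on-study, a missing day in the dosing month is set to the dosing day (SAP Appendix A), and Day 1 events before the injection count as on-study. The loss concerns events with a known pre-dose onset.
- *That all worsening is lost.* This depends on whether worsening opens a new record. Protocol Appendix B and the eCRF guidance were not in the text available, so their silence cannot be assumed. Protocol 8.3.5 already sends aggravated examination findings, and clinically relevant laboratory or vital-sign deterioration, to AE reporting. The SAP's wording that "the maximum intensity will be taken as the highest recorded maximum intensity" does not settle it, because that sentence concerns several occurrences of the same AE.
- *That the SAP contradicts Protocol 9.4.3.* Protocol 9.4 leaves technical detail to the SAP, and limiting tables to on-study events is a permissible detail.

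**Conclusion.** The point holds for events that become serious. Followed exactly, the SAP omits from its AE, SAE, causality and intensity, and investigator-driven AESI summaries an event with pre-dose onset that first becomes serious on or after the dose date. This is a stated rule that gives a wrong count, although the date needed to correct it is collected.

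The conclusion assumes that the event stays one record with a known pre-dose onset date. The consequence is one child in 14, or 7.1 percentage points per case, and a possible change from no SAEs to one. The expected frequency is low: well under one child on the assumptions in the working. For non-serious worsening, the documents support only a request to confirm the recording convention.

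**What to change.** In SAP 3.4.1, 4.2.6.1 and Appendix B, add that an AE with onset before dosing is also counted as on-study if the date it met seriousness criteria is on or after the dose date.

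For worsening that does not become serious, confirm in the eCRF completion guidance that an increase in severity after dosing is entered as a new AE record dated at the worsening. The existing onset rule then captures it. A SAP rule alone would not do this, because the AE variables listed in Protocol 8.3.2 include no date of severity change.

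The cost is SAP wording and a line of guidance, with no new visit, sample or CRF field. The downsides are a slightly higher on-study AE and SAE count and possible queries on records already entered.

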3.1.4 Visit Windows

Summaries and analyses for which data are presented by study day (e.g. “Day 1”) will use the analysis visit windows to classify the data record, which is derived from the assessment date relative to the date of IP administration. Study Day is defined as specified in Section 3.1.2, unless specified otherwise.

Visit window is allowed only for the visits specified in Table 1.

Table 1 Visit windows allowed

Visit	Target Day	Visit Window
V4	Day 7	4-8
V5	Day 11	9-12
V6	Day 15	13-21
V7	Day 29	22-42
V8	Day 57	43-70
V9	Day 85	71-88

Nominal database visit numbers will not be used in any summary or analysis by visit.

Any data collected at unscheduled or repeat visits will be listed and will be included in baseline definitions (see Section 3.1.1), and in any definitions of maximum value, minimum value or last value within the relevant study period.

Measurements collected from unscheduled visits, repeat assessments or early study discontinuation visits may also be considered in the analysis visit window. In the case of a missing value at a scheduled visit, which is then followed by a non-missing value at an unscheduled or repeat assessment within the same visit window, the non-missing value at the unscheduled/repeat assessment will be used.

If a subject has more than one non-missing value within the same visit window, the following rules will apply:

- The non-missing value closest to the target day will be selected for analysis at that visit,
- If two non-missing values are the same distance from the target day, the earlier of the two values will be selected for analysis at that visit,
- If two non-missing values are recorded on the same day and have a different assessment time associated with both of them, the value with the earliest assessment time will be selected for analysis at that visit,
- If two non-missing values (for continuous variables) are recorded on the same day and have no assessment time associated with at least one of them, or the same assessment time associated with both of them, the average of the two values will be selected for analysis at that visit. For categorical variables in this situation, the worst case will be used.

If a subject has no value within a particular visit window, then the subject will have a missing value on that CSP scheduled study day in summaries and analysis.

3.1.5 Prior and concomitant medications

Medications or therapies will be classified per the World Health Organization (WHO) Drug Reference List dictionary which employs the Anatomical Therapeutic Chemical (ATC) classification system.

A medication will be regarded as prior if it was stopped on or before the IP dose date (medication stop date \leq IP dose date).

A medication will be regarded as concomitant if the start date is on or after the IP dose date, but prior to the end of study period (IP dose date \leq medication start date \leq study completion or withdrawal date), or if it started on or prior to the IP dose date and was ongoing after the IP dose date.

The handling of partial/missing dates for prior/concomitant medications is detailed in [Appendix A](#).

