6.5 Concomitant Therapy

Throughout the study, Investigators may prescribe concomitant medications or treatments (including rescue medication as required) deemed necessary to provide adequate supportive care. All use of concomitant medications and supplements (nutritional and prophylactic) will be recorded on the concomitant medication eCRF.

Any medication or vaccine (including over-the-counter or prescription medicines, vitamins and/or herbal supplements) that the subject is receiving at the time of enrolment or receives during the study must be recorded along with:

- Reason for use
- Dates of administration including start and end dates
- Dosage information including dose and frequency.

Refer to Section 8.1.1.1 for details of maintenance therapy restrictions on the days when lung

function testing is performed and to Section 8.1.2 for restrictions prior to the **CCI** test.

Asthma worsenings/exacerbations should be treated with oral, inhaled, or other medications (including corticosteroids and rescue medication) according to standard practice. The decision and the administration may be at the discretion of the Investigator and/or parent/legal guardian/subject upon temporary worsening of asthma signs and symptoms. In cases of asthma worsening/exacerbation, subjects should be evaluated at the study centre when feasible.

All medications taken for asthma or other conditions in the 6 months prior to Visit 1 must be recorded in the eCRF along with reason for treatment by the Investigator/authorised delegate at each visit.

The CRO Medical Monitor should be contacted if there are any questions regarding concomitant or prior therapy.

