9.4.1 General Considerations

No formal statistical hypothesis tests will be made. Data will be provided in data listings

sorted by subject number. Tabular summaries will be presented. Categorical data will be summarised by the number and percentage of subjects in each category. Continuous variables will be summarised by descriptive statistics, including number of subjects, mean, standard deviation, median, minimum and maximum for non-PK data. Median will be presented together with first and third quartile if appropriate. For the summary of PK concentration levels, in addition, geometric mean and coefficient of variation (CV%) based on log-transformed data will be presented. Unless otherwise stated, all summary tables will present descriptive statistics and/or frequency by visit.

Frequency and percentages of subject disposition and reasons for withdrawal from the study will be presented. Subjects who withdraw from the study will be listed along with the reason for discontinuation.

Frequency and percentages of subjects in each analysis population will be provided.

Demographics and subject characteristics will be summarised using frequency and percentages (for categorical variables) and n, mean, standard deviation, minimum, median and maximum (for continuous variables) using both the PK and safety analysis set.

Relevant medical history/current medical conditions will be coded using the version in force at DBL of the Medical Dictionary for Regulatory Activities (MedDRA) and summarised by system organ class (SOC) and preferred term (PT) using frequency and percentage of subjects. Virology results obtained at screening will be summarised using frequency and percentage of subjects presenting HBsAg, HCAb, HIV-1 and HIV-2.

Prior and concomitant medications, categorised according to the World Health Organization (WHO) Drug Reference List dictionary which employs the Anatomical Therapeutic Chemical (ATC) classification system, will be summarised as frequency and percentage of subjects reporting usage. Prior medications are defined as those which stopped before IP. Concomitant medications are defined as those which either started or continued after IP.

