1 STUDY DETAILS

This is the statistical analysis plan (SAP) for study D5180C00025. The SAP describes the statistical analyses specified in version 4.0 of the clinical study protocol (CSP) in more detail; any changes with regards to what is already specified in the CSP will be described in [Section 6](#) of this document.

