8 APPENDIX

Appendix A Handling Incomplete Dates for Adverse Events and Medications

Dates missing the day or both the day and month of the year will adhere to the following conventions in order to classify on-study AEs and to classify prior and concomitant medications.

In general, listings will present the actual partial or missing values rather than the imputed values that may be used in derivation. In instances where imputed values will be presented, impute values will be flagged.

Adverse Events

- The missing day of onset of an AE will be set to:
 - First day of the month that the event occurred, if the onset YYYY-MM is after the YYYY-MM of IP dosing
 - The day of IP dosing, if the onset YYYY-MM is the same as YYYY-MM of IP dosing
 - The date of informed consent, if the onset YYYY-MM is before the YYYY-MM of IP dosing.
- The missing day of resolution of an AE will be set to:
 - The last day of the month of the occurrence. If the subject died in the same month, then set the imputed date as the death date.
- If the onset date of an AE is missing both the day and month, the onset date will be set to:
 - January 1 of the year of onset, if the onset year is after the year of IP dosing.
 - The date of IP dosing, if the onset year is the same as the year of IP dosing.
 - The date of informed consent, if the onset year is before the year of IP dosing.
- If the resolution date of an AE is missing both the day and month, the date will be set to:
 - December 31 of the year of occurrence. If the subject died in the same year, then set the imputed date as the death date.

Prior/concomitant medication

Dates missing the day or both the day and month of the year will adhere to the following conventions in order to classify prior/concomitant medications:

- The missing day of start date of a therapy will be set to the first day of the month of the occurrence.
- The missing day of end date of a therapy will be set to the last day of the month of the occurrence.

- If the start date of a therapy is missing both the day and month, the onset date will be set to January 1 of the year of occurrence.
- If the end date of a therapy is missing both the day and month, the date will be set to December 31 of the year of occurrence.
- If the start date of a therapy is null and the end date is not a complete date, then the start date will be set to the date of the first study visit.
- If the start date of a therapy is null and the end date is a complete date:

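### SAP 3.1.5 puts the dose date in both medication classes, so some Day 1 drugs are labelled against protocol 9.4.1, and SAP Section 6 does not declare the change

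*SAP*

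**What the plan says.** Protocol 9.4.1 defines the two classes by reference to the investigational product (IP): "Prior medications are defined as those which stopped before IP", and "Concomitant medications are defined as those which either started or continued after IP". It plans a summary of the frequency and percentage of subjects using each class.

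SAP 3.1.5 works with the dose date instead. "A medication will be regarded as prior if it was stopped on or before the IP dose date". "A medication will be regarded as concomitant if the start date is on or after the IP dose date" and not later than study completion or withdrawal, or "if it started on or prior to the IP dose date and was ongoing after the IP dose date".

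On the data available, protocol 6.5 asks for "Dates of administration including start and end dates" for each medication and lists no clock time. Protocol 6.4 does ask for the date and time of IP administration.

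On departures from the protocol, SAP Section 1 says that "any changes with regards to what is already specified in the CSP will be described in" Section 6. Section 6 lists only the Day 29 PK analysis.

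For incomplete dates, SAP Appendix A has a rule for a missing start with a partial end: "start date of a therapy is null and the end date is not a complete date, then the start date will be set to"; its target is the first study visit. The next rule, for a missing start with a complete end date, checks whether the end falls after the first visit and, if it does not, sets the start equal to the end.

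**The concern.** This is a single-dose study, so Day 1 is the only boundary between the two classes, and the SAP rule is ambiguous on exactly that day. Medications confined to Day 1 are foreseen by the protocol. Numbing agents may be used with the injection (6.2.1), as-needed short-acting beta-agonist is allowed (Table 5), and drugs to treat an acute reaction must be at hand (8.3.11).

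Under the SAP, a drug given after the injection and finished the same day is labelled prior as well as concomitant. A course that began earlier and ended on Day 1 after the injection is labelled prior only. Either label conflicts with the protocol. A subject could be counted in both halves of a prior/concomitant summary for one single-day use, or left out of the half where the protocol puts the use.

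**Working it through.** No figure in the plan needs reproducing; the check is one of logic. Write D for the dose date, S for the start date and E for the stop date, with S ≤ E.

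**Rules as written**
- SAP prior: E ≤ D.
- SAP concomitant: D ≤ S ≤ study end, or S ≤ D with E > D.
- Protocol prior: stopped before the injection.
- Protocol concomitant: started or continued after the injection.

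**Where the SAP classes overlap.** Prior needs E ≤ D, which rules out the second concomitant limb (E > D). The first limb needs S ≥ D. Together, D ≤ S ≤ E ≤ D, so S = E = D. A check of every date pair from 30 days before to 30 days after D (61 × 62 / 2 = 1,891 pairs) found the overlap at that pair only.

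**Cases side by side**

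| Medication | SAP 3.1.5 | Protocol 9.4.1 | With the fix |
|---|---|---|---|
| Started and stopped on Day 1, after the injection | Prior and concomitant | Concomitant | Concomitant |
| Started on Day 1 after the injection, stopped on Day 3 | Concomitant | Concomitant | Concomitant |
| Started before Day 1, stopped on Day 1 after the injection | Prior | Concomitant | Concomitant |
| Started and stopped on Day 1, before the injection | Prior and concomitant | Prior | Concomitant |
| Stopped before Day 1 | Prior | Prior | Prior |
| Ongoing throughout | Concomitant | Concomitant | Concomitant |

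The SAP departs from the protocol in the first, third and fourth rows, all with a stop date of Day 1. The fix removes the overlap and corrects the first and third rows. The fourth stays different, because dates alone cannot separate use before the injection from use after it.

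**Does a date-level reading of the protocol rescue the SAP?** No. If the protocol's reference to IP is read as the dose date, prior means E < D, so a medication with E = D is still not prior.

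**Appendix A.** Assume, for illustration, a first visit on 5 March 2022 and a dose on 15 March 2022. A therapy with no start date and an end of January 2022 has its end imputed to 31 January and its start to 5 March, which is 33 days after its end. Protocol 6.5 asks for medications in the 6 months before Visit 1, so such records can occur. The class is not affected: 31 January is before 15 March, so the therapy is prior. If the end is imputed first and the complete-date rule then applied, 31 January is not after 5 March, so the start becomes 31 January. The order is restored and the class is unchanged.

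**The case against.** The strongest reply is that little depends on the label. SAP 4.2.2 tabulates allowed and disallowed medications by study period, and SAP 3.1.3 ends screening the day before IP and starts the on-study period on the IP date. Those periods do not overlap, so use on Day 1 belongs to the on-study period whatever 3.1.5 calls it. For the prior and concomitant classes, SAP 4.2.2 specifies only a listing. This stands, and it limits the point to that listing and to any summary produced under protocol 9.4.1.

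It is also fair that the SAP works at the resolution of the data. Protocol 6.5 lists only dates for medications, so using dates is not the fault; including the dose date on both sides is. No new eCRF field is needed to correct that.

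Two stronger readings are tempting, and the documents do not support them:

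- A reader might infer that treatment of an acute reaction on Day 1 would be missed in the safety review. Adverse events are assigned to periods by onset date (SAP 3.4.1). Anaphylaxis is identified from a modified standardised query with timing relative to the injection, followed by medical review, and injection site reactions come from the adverse event page (Appendix B). None of these uses the prior/concomitant class.
- A reader might infer that the Appendix A rule creates false breaches of the washout criteria, or false entries in the screening-period table. Deviations are defined in a separate plan (SAP 2.2), and disallowed medications are settled by physician review of drug codes and names (SAP 4.2.2). Listings generally show the actual partial dates and flag any imputed ones. Nothing in the SAP says that an imputed start alone places a medication in a period when its end came earlier.

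**Conclusion.** The point holds as an error of definition with limited effect. SAP 3.1.5 contradicts protocol 9.4.1 for medications with a stop date of Day 1, and Section 6 does not declare the change. The double label arises only when start and stop are both the dose date; the prior-only error arises only when an earlier therapy is used after the injection and stopped that day.

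The documents do not say how many records this will involve, so no percentage can be given. The conclusion rests on the wording of the two definitions and holds whether the protocol's split is read at the level of time or of date. PK endpoints, adverse event and special-interest outputs, and the period-based medication tables are not affected. The Appendix A rule is a minor inconsistency between neighbouring rules and changes no classification.

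**What to change.** - **SAP 3.1.5.** Define prior as a stop date strictly before the IP dose date. Define concomitant as any medication that is ongoing or has a stop date on or after the IP dose date, with a start date no later than study completion or withdrawal.
- **SAP Section 6.** State that, because only dates are collected for medications, use on Day 1 before the injection is counted as concomitant, and that this differs from protocol 9.4.1.
- **SAP Appendix A.** For a missing start with a partial end date, impute the end date first and then apply the existing complete-date rule, so that an imputed start never falls after the imputed end.

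The cost is a few sentences in the SAP and the matching derivation code, with no new data collection. The small downside is that drugs used only before the injection on Day 1, such as numbing agents, are labelled concomitant. That agrees with SAP 3.1.3, which already places the whole of the dose date in the on-study period.
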